1.4.2 Dose Selection Rationale

Study CN170003 was a double-blind, randomized, placebo-controlled, dose-ranging trial of rimegepant for the acute treatment of migraine [2]. The primary objective was to evaluate the efficacy of rimegepant compared with placebo in the acute treatment of migraine as measured by pain freedom (head pain intensity level reported as “no pain”) at 2 hours post-dose using a four point rating scale (no pain, mild pain, moderate pain, severe pain) while identifying an optimal dose to support the Phase 3 clinical trials. Subjects were randomized to receive placebo, sumatriptan 100 mg or rimegepant (10, 25, 75, 150, 300, or 600 mg). Randomization made use of an adaptive design, whereby one quarter of subjects were assigned placebo and one-eighth were assigned sumatriptan; the remainder were assigned to one of the six rimegepant groups based on a Bayesian analysis of the observed response rates. Subjects were instructed to treat one migraine of moderate or severe pain intensity and return to the clinic within 7 days.

A total of 885 subjects were randomized and 812 completed the study. Key entry criteria were very similar to those chosen for this clinical trial.

A comprehensive and durable efficacy profile for rimegepant was demonstrated to be fully present at 75 mg but not at lower doses (i.e., 10 mg or 25 mg). This dose was selected as the optimal dose to support Phase 3 clinical trials, given that larger doses (150 mg, 300 mg, 600 mg) showed a similar efficacy profile and there was no pattern of added benefit in dosing higher, consistent with previously published migraine studies [8]. rimegepant at 75 mg showed statistically significant broad efficacy across all four traditional endpoints at 2 hr (pain, nausea, photophobia and phonophobia) which was durable and persisted through 24 hr. At 2 hr following a single oral dose of 75 mg, patients who previously were experiencing moderate-to-severe migraine pain had no-pain (31.4% $p = 0.0018$) or mild-to-no-pain (72.1%) as compared to placebo (15.3% and 51.2%, respectively). For the 75 mg dose at 2 hr, patients also showed significant freedom from nausea (67.4%, $p = 0.0074$) freedom from phonophobia (52.3%, $p = 0.0001$) and freedom from photophobia (41.9%, $p = 0.0023$) vs. placebo (51.2%, 28.1%

and 24.1%, respectively). The lasting nature of these beneficial anti-migraine effects were evidenced by a comparatively similar efficacy profile in the 2-24 hr measures, where rimegepant at 75 mg produced significant 2-24 hr sustained pain freedom (27.9%, $p < 0.0001$) and 2-24 hr sustained pain relief (69.8%, $p < 0.0001$) vs. placebo (7.4% and 42.4%, respectively).

1.4.3 Other Rationale related to the compound/study

Prior to initiation of Phase 3, a Phase 1 crossover study to assess the safety, tolerability and pharmacokinetics of a single dose of the rimegepant tablet in healthy volunteers will be conducted to ensure PK comparability with the previously studied capsule (rimegepant free-base). The Investigator Brochure will be updated to include these study results when available.

1.5 Research Hypothesis

Rimegepant (75mg tablet) will have efficacy superior to placebo in the treatment of acute migraine with a favorable safety profile suitable for use by a broad patient population.

2 STUDY OBJECTIVES

2.1 Primary

To evaluate the efficacy of rimegepant (75 mg tablet) compared with placebo in the acute treatment of migraine as measured by **pain freedom** and by **freedom from the most bothersome symptom** (MBS), associated with migraine, at two hours post dose.

2.2 Secondary

- To evaluate rimegepant (75 mg tablet) compared to placebo on **freedom from photophobia** at 2 hours post-dose.
 - To evaluate rimegepant (75 mg tablet) compared to placebo on **freedom from phonophobia** at 2 hours post-dose.
 - To evaluate rimegepant (75 mg tablet) compared to placebo on **pain relief at 2 hours** post-dose.
 - To evaluate rimegepant (75 mg tablet) compared to placebo on **freedom from nausea** at 2 hours post-dose
 - To evaluate rimegepant (75 mg tablet) compared to placebo on the **probability of requiring rescue medication** within 24 hours of initial treatment.
 - To evaluate rimegepant (75 mg tablet) compared to placebo on **sustained pain freedom** from 2 to 24 hours post-dose
 - To evaluate rimegepant (75 mg tablet) compared to placebo on **sustained pain relief** from 2- 24 hours post-dose.
 - To evaluate rimegepant (75 mg tablet) compared to placebo on **sustained pain freedom** from 2- 48 hours post-dose..
 - To evaluate rimegepant (75 mg tablet) compared to placebo on **sustained pain relief** from 2- 48 hours post-dose.
 - To evaluate rimegepant (75 mg tablet) compared to placebo for the incidence of **pain relapse** from 2 to 48 hours post-dose
-

- To evaluate the effect of rimegepant (75 mg tablet) relative to placebo on the patients ability function at a “normal” level at 2 hrs post dose according to the **Functional Disability** scale.

2.3 Exploratory

- To evaluate the effect of rimegepant (75 mg tablet) relative to placebo on the patients ability to work or function at 24 hrs post dose according to the Functional Disability scale.
 - To evaluate rimegepant (75 mg tablet) compared to placebo on **pain relief at 90** minutes post-dose.
 - To evaluate rimegepant (75 mg tablet) compared to placebo on **pain relief at 60** minutes post-dose.
 - To evaluate rimegepant (75 mg tablet) compared to placebo on **pain relief at 30** minutes post-dose.
 - To evaluate the effect of rimegepant (75 mg tablet) relative to placebo on the **Migraine Preference of Medication (PoM)**
 - To evaluate rimegepant (75 mg tablet) relative to placebo for pain relief on the 4 point scale at all scheduled time points post dose
 - To evaluate the effect of rimegepant (75 mg tablet) relative to placebo on the **Migraine Quality of Life (MQoLQ)**
 - To evaluate the **tolerability and safety** of rimegepant (75 mg tablet) in the acute treatment of migraine as measured by the frequency of adverse events of at least moderate intensity, serious adverse events; and clinically relevant laboratory abnormalities.
 - To evaluate the effect of rimegepant (75 mg tablet) relative to placebo on the **Sheehan Suicidality Tracking Scale**.
-

3 STUDY ENDPOINTS

3.1 Primary

Pain freedom will be assessed using the number of evaluable subjects that report no pain at 2 hours post-dose. Pain will be measured on a 4 point Likert scale (0=none, 1=mild, 2=moderate, 3=severe).

Freedom from the most bothersome symptom (MBS) will be assessed using the number of evaluable subjects that report the absence of their MBS at 2 hours post-dose. The MBS (nausea, phonophobia or photophobia) will be measured using a binary scale (0=absent, 1=present).

3.2 Secondary

- **Freedom from Photophobia** will be assessed by tabulating the number of subjects that report the absence of photophobia at 2 hours post-dose in the subset of subjects that reported the presence of photophobia at headache baseline.
 - **Freedom from Phonophobia** will be assessed by tabulating the number of subjects that report the absence of phonophobia at 2 hours post-dose in the subset of subjects that reported the presence of phonophobia at headache baseline.
 - **Pain Relief** (aka “headache response”), at 2 hours post-dose, will be assessed using the number of evaluable subjects that report a pain level of moderate or severe (responses of 2 or 3 on the 4 point Likert scale) at baseline and then report a pain level of none or mild (response of 0 or 1) at two hours post-dose.
 - **Freedom from Nausea** will be assessed by tabulating the number of subjects that report the absence of nausea at 2 hours post-dose in the subset of subjects that reported the presence of nausea at headache baseline.
 - The probability of **requiring rescue medication** will be assessed using the number of subjects that take rescue medication within 24 after administration of study medication (BHV3000 or placebo).
 - **Sustained pain freedom**, from 2 to 24 hours, will be assessed using the number of subjects that do not experience any headache pain through the time period of interest.
-

- **Sustained pain relief**, from 2 to 24 hours will be assessed using the number of subjects that do not use any rescue medications, and do not experience any moderate or severe headache pain through the time period of interest.
- **Sustained pain freedom**, from 2 to 48 hours, will be assessed using the number of subjects that do not experience any headache pain through the time period of interest
- **Sustained pain relief** from 2 to 48 hours, will be assessed using the number of subjects that do not use any rescue medications, and do not experience any moderate or severe headache pain through the time period of interest.
- **Pain relapse** will be assessed using the number of subjects that are pain free at 2 hours post-dose and then have a headache of any severity (response of 1, 2 or 3 on the 4 point scale) within 48 hours after administration of study medication (BHV3000 or placebo).
- The proportion of subjects able to function normally, at 2 hours, will be assessed using the number of subjects that self-report as “normal” on the **functional disability** scale.

3.3 Measures of Interest

Safety and Other assessments:

[figure not shown]
- Adverse Events
 - ECG assessments
 - Vital Sign and Physical Measurements
 - Routine Laboratory Tests
 - Sheehan Suicidality Tracking Scale (S-SST)
 - Preference of Medication (PoM)
 - Assessment of Migraine Pain and Symptoms
 - Migraine Specified Quality of Life Questionnaire (MQoLQ)
-

4 STUDY PLAN

4.1 Study Design and Duration

This is a double-blind, randomized, multicenter, outpatient evaluation of the safety and efficacy of rimegepant as compared to placebo in the treatment of moderate or severe migraine. Participants will be dispensed one dose of study medication consisting of a rimegepant 75 mg tablet or a matching placebo. The total duration of the study will be approximately 11 weeks. This includes a 3-28 day Screening Period, an Acute Phase that can last up to 45 days or until the patient has a migraine that reaches moderate or severe intensity, followed by an End of Treatment Visit 7 days after the administration of the study medication.

4.2 Study Schematic

4.3 Schedule of Assessments

Table 1: Schedule of Assessments

Procedure	Screening Visit (3-28 days)¹	Baseline Visit (Randomization)¹	Onset of moderate or severe migraine²	During Treatment 15, 30, 45, 60 and 90 minutes Post-Dose	During Treatment 2, 3, 4, 6, 8 hours Post- Dose	During Treatment 24 hours Post-Dose	During Treatment 48 hours Post- Dose	End of Treatment Visit
Eligibility Assessments								
Informed Consent	X							
Inclusion/Exclusion Criteria	X	X						
Medical History	X							
Prophylactic Migraine Medication/ Concomitant Medication ³	X	X						X
Assessment of Migraine History (Signs and symptoms) paper source ¹⁴	X							
Safety Assessments								
Physical Examination	X							X
Vital Signs/Physical Measurements ⁴	X	X						X
Clinical Safety Laboratory Testing ⁵	X							X

Procedure	Screening Visit (3-28 days)¹	Baseline Visit (Randomization)¹	Onset of moderate or severe migraine²	During Treatment 15, 30, 45, 60 and 90 minutes Post-Dose	During Treatment 2, 3, 4, 6, 8 hours Post-Dose	During Treatment 24 hours Post-Dose	During Treatment 48 hours Post-Dose	End of Treatment Visit
ECG	X							X
Pregnancy Test ⁶	X	X	X					X
Adverse Event and Serious Adverse Event Assessment ⁷	X	X	X	X	X	X	X	X
Sheehan Suicidality Tracking Scale ⁸	X	X						X
Clinical Drug Supplies/Study Supplies								
Randomize ⁹		X						
Dispense Study Medication		X						
Administer 1 dose of study medication ¹⁰			X					
Return unused study medication								X
eDiary returned/reviewed for completeness ¹¹								X
Efficacy Assessments¹²								
Assessment of migraine pain ¹³			X	X	X	X	X	

Procedure	Screening Visit (3-28 days)¹	Baseline Visit (Randomization)¹	Onset of moderate or severe migraine²	During Treatment 15, 30, 45, 60 and 90 minutes Post-Dose	During Treatment 2, 3, 4, 6, 8 hours Post-Dose	During Treatment 24 hours Post-Dose	During Treatment 48 hours Post-Dose	End of Treatment Visit
Assessment of Migraine Symptoms (photophobia, phonophobia, and nausea - eDiary) ¹³			X	X	X	X	X	
Functional Disability Scale ¹³			X	X	X	X	X	
MQoLQ (Migraine Specified Quality of Life Questionnaire) ¹³						X		
Preference of Medication ¹³						X		

¹ **Screening/Baseline Phase** will be 3 - 28 days. The **Baseline Visit** may be scheduled but should only occur *after* all screening procedures are complete, patient meets inclusion/exclusion criteria, and lab test results have been received by the site.

² Patients will use eDiary to answer questions about their migraine symptoms upon experiencing a moderate/severe migraine headache. The patient will administer pre-dispensed study drug if 1) the headache remains moderate or severe; 2) the patient has completed all required migraine assessment questions in the eDiary, including their current most bothersome migraine symptom, and 3) the patient has not already taken prohibited medications (see protocol section 5.4).

³ Patients should keep track of their concomitant medications throughout the study and report them to the study personnel at the End of Treatment Visit. Any medication taken for recurrent headache should be documented. Use of concomitant medications after randomization, including rescue medications, will be recorded by the patient on a paper diary and reported to the site.

⁴ Height will only be captured at the Screening Visit. Weight body temperature, respiratory rate, blood pressure and heart rate will be collected at all time points where indicated. Sitting arterial systolic and diastolic blood pressure and pulse rate will be measured.

⁵ All Screening Visit laboratory test results must be received prior to Baseline Visit.

⁶ A serum pregnancy test will be completed at Screening and End of Treatment Visits as part of the standard laboratory tests (if appropriate). Confirmatory urine pregnancy test for WOCBP should be completed on site at Baseline Visit and any subsequent visits for confirmation at the Investigator's discretion. Home pregnancy test will be provided to WOCBP after completion of baseline visit.

⁷ SAEs are reported from the time of informed consent and non-serious AEs are reported from baseline. All ongoing non-serious AEs and SAEs will be followed to resolution or until investigator deems there will be no further status change. SAE and AE's that occur during the treatment period should be reported to the site.

⁸ This scale will be clinician administered, completed on site, and will be in paper. The source document will be provided by Biohaven. The assessment period for completing the scale will be 30 days prior to Screening, and since the last visit for the remainder of the study.

⁹ Patients will be randomized in the IWRS system at the Baseline Visit (Randomization Day 01)

¹⁰ Patient should be instructed that the dose should be taken once the migraine attack reaches moderate or severe pain.

¹¹ Site staff to review and confirm entries with patients and confirm all data points are transferred to the system and reset eDiary for future patient use, PRIOR to the patient leaving the clinic.

¹² ± Windows for timeframe around efficacy assessments (15, 30, 45, 60, 90 min, 2, 3, 4, 6, 8, 24 and 48 hours) will be automated and captured in the eDiary.

¹³ These scales will be captured in the eDiary. Patients will also be asked about their most bothersome symptom at the time of reporting and treating a qualifying migraine.

¹⁴ Paper source document will be used to capture Migraine History. Patients will also be asked about their typical most bothersome symptom when having a migraine.

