dosing. Patients who have headache pain reduced to a mild intensity or pain free intensity level will be considered to have achieved pain relief.

After dosing with study medication, all other headache medication is prohibited during the 2 hours post dose. However, a patient who does not experience relief of their migraine headache at the end of two hours after dosing with study medication (and after the two hour assessments have been completed on the eDiary) will be permitted to use the following rescue medication: aspirin, ibuprofen, acetaminophen up to 1000mg/day (this includes Excedrin Migraine) naproxen (or any other type of nonsteroidal anti-inflammatory (NSAID)), antiemetics (e.g., metoclopramide or promethazine), or baclofen. These are the only medications allowed for rescue treatment after 2 hours post dose of study medication. However, if needed, after 48-hours of administering the one dose of study medication (and before returning for the End of Treatment Visit) patients may take their prescribed standard of care medications for treatment of migraine, including triptans if not contraindicated, **provided all of the assessments have been completed on the eDiary**. Exclusionary rescue medication such as, opioids, ergotamines, butalbital compounds, and muscle relaxants (except baclofen as a rescue medication, see above) are not allowed on this study. Similarly, if the migraine is relieved by study medication at 2 hours after dosing but then recurs to a moderate or severe intensity level between two and forty-eight hours, the patient will be permitted to take the same rescue therapy as outlined above. In all circumstances, the patient will continue to complete his or her eDiary for up to forty-eight hours after consuming the study medication.

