5.4 Prohibited Concomitant Medication

The below medications are prohibited prior to randomization and during the course of this study or as specified.

1. St. John's Wort should not be taken 14 days prior to randomization and throughout the study.
2. Butterbur root or extracts should not be taken 14 days prior to randomization and throughout the study.
3. History of use of ergotamine medications on greater than/equal 10 days per month on a regular basis for greater than/equal 3 months
4. History of non-narcotic analgesic intake on greater than/equal 15 days per month for greater than/equal 3 months
5. Use of narcotic medication, such as barbiturates, heroin, opium in the form of morphine and codeine, oxycodone and hydrocodone for at least 2 days prior to randomization.
6. Use of acetaminophen or acetaminophen containing products at daily dosing levels greater than 1000mg/day for at least two days prior to randomization.
7. Use of marijuana is prohibited during the study.

Patients on prophylactic migraine medication are permitted to remain on therapy provided they have been on a stable dose for at least 3 months prior to study entry.

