5.4.1 Rescue Medications

After dosing with study medication, all other headache medication is prohibited during the 2 hours post dose. However, a patient who does not experience relief of their migraine headache at the end of two hours after dosing with study medication (and after the two hour assessments have been completed on the eDiary), will be permitted to use the following rescue medication: aspirin, ibuprofen, acetaminophen up to 1000mg/day (this includes Excedrin Migraine) naprosyn (or any other type of non-steroidal anti-inflammatory (NSAID)), antiemetics (e.g., metoclopramide or promethazine), or baclofen. These are the only medications allowed for rescue treatment after 2 hours post dose of study medication. However, if needed, after 48-hours of administering the one dose of study medication (and before coming in for the End of Treatment Visit) patients may take their prescribed standard of care medications for treatment of migraine (including triptans if not contraindicated, **provided all of the assessments have been completed on the eDiary**). Similarly, if the migraine is relieved by study medication at 2 hours after dosing but then recurs to a moderate or severe intensity level between two and forty-eight hours, the patient will be permitted to take the same rescue therapy as outlined above. In all circumstances, the patient will always continue to complete his or her eDiary for up to forty-eight hours after consuming the study medication. Use of concomitant medication after randomization, including rescue medication, will be recorded by the patient on a paper diary and reported to the site. The site will record medications that were taken within 14 days of dosing with study medication (or until the End of Treatment Visit).

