5.7.1 Rescue Medication

Subjects who take rescue medication as recorded on the CRF or any medication used for headaches as recorded anywhere on the CRF or eDiary will be considered as failures for any efficacy evaluations that are coincident or follow the administration of the rescue medication/other headache medication. If the time of rescue medication is missing, subjects will be considered as failures for any efficacy evaluations are on or after the date of administration of the rescue medication/other headache medication/other headache medication.

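### The dosing condition lets a patient take study drug after treating the same attack with a triptan, NSAID, antiemetic or low-dose acetaminophen, and SAP 5.7.1, which has no start time, then scores that patient a 2-hour failure

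*Protocol*

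**What the plan says.** Table 1 footnote 2 (Protocol 4.3) allows dosing when the headache is still moderate or severe, the eDiary questions including most bothersome symptom (MBS) are answered, and "3) the patient has not already taken prohibited medications (see protocol section 5.4".

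Section 5.4 opens "The below medications are prohibited prior to randomization and during the course of this study or as specified" and has seven items: St. John's Wort, butterbur, a history of frequent ergotamine use, a history of frequent non-narcotic analgesic use, narcotics, acetaminophen above 1000 mg/day, and marijuana. The narcotic item ends "oxycodone and hydrocodone for at least 2 days prior to randomization" and the acetaminophen item "greater than 1000mg/day for at least two days prior to randomization". Section 5.4.1 adds: "After dosing with study medication, all other headache medication is prohibited during the 2 hours post dose".

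On recording, footnote 3 says: "Use of concomitant medications after randomization, including rescue medications, will be recorded by the patient on a paper diary". Section 5.4.1 also has sites record medication taken within 14 days of dosing.

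SAP 5.7.1 provides that subjects who take rescue medication or "any medication used for headaches as recorded anywhere on the CRF or eDiary will be considered as failures for any efficacy evaluations" that coincide with or come after that use. RM=F in SAP 2.3, which SAP Table 1 applies to both co-primaries, names rescue medication only.

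**The concern.** Patients must wait until pain is moderate or severe before dosing, and some will take their usual drug while they wait. A patient who takes ibuprofen, still has moderate pain and answers the eDiary questions meets all three conditions. That patient takes study drug and, with one post-baseline efficacy data point, enters the mITT population (SAP 4.1).

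The protocol has then admitted an attack that the analysis has already decided. If the ibuprofen is recorded as headache medication, both 2-hour co-primaries are failures whatever study drug does. If it is not recorded, the 2-hour response mixes two drugs. Either way, the reported risk difference is not quite the effect of rimegepant in an otherwise untreated attack. None of the sensitivity analyses in SAP 5.7.3.1 and 5.7.3.2 varies this rule.

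**Working it through.** **1. What 5.4 covers for the treated attack.**

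- Triptans, NSAIDs, antiemetics: no item bars use earlier in the attack.
- Non-narcotic analgesics and ergotamines: listed only as overuse histories.
- Acetaminophen: only above 1000 mg/day, and counted back from randomization, which can be up to 45 days before the dose.
- Narcotics: also counted back from randomization. Coverage afterwards is ambiguous rather than absent, because of the scope sentence of 5.4 and because 4.3.2 says "opioids, ergotamines, butalbital compounds, and muscle relaxants (except baclofen as a rescue medication, see above) are not allowed on this study".
- All other headache medication: barred by 5.4.1, but only from the dose onward.

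**2. How far back 5.7.1 reaches.** The rule has an end (the evaluation) but no start. SAP 5.2.8 treats medication from 14 days before the dose as concomitant, so earlier headache medication is in the database. Inclusion criteria 2c and 2e admit 2 to 8 moderate or severe attacks a month. With a 30-day month that is 2 × 14/30 = 0.9 to 8 × 14/30 = 3.7 attacks in such a window. Taken literally, the rule would fail many patients for an earlier attack. It would also fail everyone on recorded migraine prophylaxis, making the risk difference in that stratum zero by construction. SAP 5.7.3.1 asks for a risk difference in each stratum, so this cannot be intended, but no sentence excludes it.

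**3. The plan's own power figure.** Inputs: Phase 2b pain freedom 31.4% vs 15.3% (Protocol 1.3.2.8), 550 per arm (Protocol 9.2), two-sided 0.05 (SAP 5.2.5). With pooled null variance,

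z = [Δ√n − 1.96√(2p̄(1 − p̄))] / √(p₁q₁ + p₂q₂) = [0.161 × 23.452 − 1.96 × 0.5983] / 0.5874 = 4.43,

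so power is 99.999%, in line with the stated figure of more than 95%. It is the same to that precision at 540 per arm (90% of 600). The joint bound is 1 − 2 × 0.05 = 90%, as stated.

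**4. Dilution when pre-dose use is recorded and scored as failure.** The documents do not give the share f of patients with such use. Assume f is equal in both arms and unrelated to response. The difference is then (1 − f) × 16.1 points. No Phase 2b MBS rate is given, so nausea (67.4% vs 51.2%, the weakest of the three symptoms) serves as a proxy.

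| Assumed f | Pain-freedom difference | Power, pain freedom | Power, nausea proxy |
|---|---|---|---|
| 2% | 15.8 | above 99.9% | 99.97% |
| 5% | 15.3 | above 99.9% | 99.94% |
| 10% | 14.5 | above 99.9% | 99.8% |
| 20% | 12.9 | 99.98% | 99.1% |

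**5. If use is not recorded.** The difference is (1 − f) × 16.1 + f × d, where d is the treatment difference among users. If d lies between 0 and 16.1, the result at f = 10% lies between 14.5 and 16.1. The limits on d are an assumption.

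**6. If the true effect is smaller than in Phase 2b.** For an illustrative 23.7% vs 15.3%, pain-freedom power falls from 94.1% without pre-dose use to 91.0% at f = 10% and 86.8% at f = 20%.

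**The case against.** The protocol does not say that condition 3 is meant to keep out every already-medicated attack. Which drugs to bar before an outpatient dose is a clinical choice, and patient instructions or eDiary screens, which are not in the documents, may already cover it. Failure scoring is the conservative choice and is the same in both arms. All of that stands. It does not remove the mismatch: as written, the protocol permits a dose that the SAP has already failed.

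Three stronger readings are tempting, and the documents do not support them.

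- A reader might infer that SAP 2.3 and 5.7.1 conflict, leaving the co-primary analysis undefined. SAP 4.2 refers the handling of rescue medication to the statistical methods section, where 5.7.1 is the operating rule. RM=F sets no post-dose limit either. The post-dose window in 5.7.4.3 defines only the 24-hour rescue endpoint. What remains is a difference in wording.
- A reader might infer that same-day use with a missing time is unhandled. SAP 5.7.1 already fails evaluations on or after the date of use, for other headache medication as well as rescue.
- A reader might infer that pre-dose use goes uncollected. The paper diary and the 14-day site record plan for it. Under-reporting is possible but is not a defect of the plan.

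**Conclusion.** The point holds as a cheap improvement, not as a threat to the trial's conclusion. The protocol's dosing condition and the SAP's failure rule do not match, and the failure rule lacks a start time and an exclusion for prophylaxis.

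Use before a blinded dose should balance between arms, so the test remains valid. Planned power survives at Phase 2b effects, subject to nausea being only a stand-in for MBS, which carries failure rules of its own. A reader might infer that the trial is underpowered. That would need both a much smaller true effect and frequent pre-dose use, and the documents give no evidence of either.

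The consequence is a risk difference moved towards zero if users are scored as failures, by a proportion equal to the share of users. That share is unknown, so the figures in the table illustrate the mechanism and do not estimate the loss.

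**What to change.** 1. Amend footnote 2 condition 3 and Protocol 5.4 so that study drug is not taken if any acute headache medication has been taken for the attack to be treated. This costs an amendment and a line in the patient instructions, and a few attacks become untreatable with study drug. It cannot affect patients already dosed: the SAP rests on Amendment 4 of 23-JAN-2018 but already splits attacks at 13-Sep-2017.
2. In SAP 5.7.1, state that the failure rule runs from onset of the treated attack and excludes stable prophylaxis. In SAP 2.3, have RM=F name rescue or other headache medication, so that the two agree. Leave the missing-time rule as it is. This costs two sentences. The change counts as prespecified only if made before unblinding. SAP 7 already reports supportive analyses in the past tense, so a later change should be labelled post hoc.
3. Optionally, repeat both co-primary analyses without subjects who took acute headache medication between attack onset and dose. Treat this as supportive only, because patients report pre-dose use after they know their outcome.
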